## MATERIALS AND METHODS

### Ethical Approval

This study was approved by the Department of Research Ethics at Simon Fraser University and conforms to the principles outlined in the Declaration of Helsinki [25]. Participants provided written informed consent and the trial was registered (Clinical.Tials.gov #NCT01567605).

### Participants

Participants were recruited using a multi-method approach. Print advertisements were circulated through our community partner, Spinal Cord Injury British Columbia, via their quarterly publication, *The Spin*, and online advertisements were posted through our institutional website ([www.icord.org](http://www.icord.org)).

Eligible participants were individuals aged >18 years of age with chronic (>1 year) traumatic high level (T6 or above) SCI, who had an established bowel care routine, and a prior history of AD. Individuals were excluded if they had a medical/psychiatric condition or substance abuse disorder, used a ventilator, had a colostomy, or did not perform regular bowel care for any reason. Additional exclusion criteria included skin breakdown in the areas receiving pressure during the bowel program, inability to communicate in English, use of medicines containing lidocaine, allergy to lidocaine, and pregnancy.

Our primary outcome measure was the difference in systolic arterial pressure between the placebo and lidocaine conditions. We determined a meaningful difference to detect in blood pressure between the two study arms of 10mmHg (based on previous unpublished observations from our lab). With a power of 0.8 and alpha of 0.05, we determined a sample size of 13 individuals would be necessary to ensure statistical confidence in our ability to detect differences in this primary outcome measure.

### Experimental Procedure

We conducted a registered double-blind placebo-controlled crossover clinical trial where participants were randomised to a series of two treatments: lidocaine lubricant (Xylocaine 2%) and standard lubricant (KY Jelly; placebo) on two consecutive at-home visits (**Figure 1**). The sequence of conditions was determined by random draw, using a complete randomised design, by a researcher external to the research team; seven participants were randomised to the lidocaine arm of the study first, and six to the placebo arm of the study first. Testing took place between August 2016 and October 2018.

Prior to the first visit, participants completed a questionnaire about their bowel management and general bowel continence [5]. On each visit, participants were fitted with a standard three-lead electrocardiogram (ECG; lead II) and a non-invasive beat-to-beat finger blood pressure monitor (Finometer Midi, Finapres Medical Systems [FMS], Amsterdam, Netherlands). After a 10-minute baseline recording (sampling rate 200Hz) participants inserted 5mL of lubricant into the rectum using a specialised device (Lube Launcher XL, CleanStream, Huntington Beach, USA) to ensure that a minimum amount of lubricant was administered. Following insertion of the lubricant, participants waited 5-min before starting bowel care (to allow for mucosal absorption of lidocaine, which has a typical onset of action of 3-5 minutes). Participants were then provided with an additional 15mL of lubricant and asked to perform their bowel care routine as

usual, replacing their normal lubricant with the lubricant provided for that day. The maximum recommended dosage of lidocaine is 600mg/12 hour. The dosage provided (20ml of 2% lidocaine) is equivalent to 400mg. The 20ml volume was determined based on discussion with bowel care providers and individuals with SCI concerning their typical lubricant needs. This dosing strategy is in line with other similar studies. Given the typical half-life of lidocaine (1.5-2 hours) we are confident there was optimal dosing throughout the duration of bowel care.

Five minutes after insertion of the test lubricant, a timer was started and the participant commenced their usual care routine. Bowel care routines were not standardised because the primary interest was to investigate the real-world feasibility and impact of this clinical recommendation in a community setting with usual participant care routines. When the participant signalled the end of their care routine (defined as the time when bowel evacuation was completed, prior to cleaning), the timer was stopped, and the bowel care duration noted. The cardiovascular monitoring equipment was then removed. Participants then completed a questionnaire specific to their bowel care on that day, reporting the method of bowel care employed as well as the severity of cardiovascular symptoms experienced [5]. Self-reported symptoms of AD were determined as described previously [5]. Two participants chose not to complete the post-bowel care questionnaire.

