### **Data analyses**

Beat-to-beat systolic (SAP) and diastolic (DAP) arterial pressures were extracted throughout the testing period. Mean arterial pressure (MAP) was calculated as  $\text{DAP} + 1/3 \times (\text{SAP}-\text{DAP})$ . Heart rate was determined from the R-R interval of the ECG. Stroke volume (SV) and cardiac output (Q) were determined using Modelflow [27,28], and total peripheral resistance (TPR) calculated as  $\text{MAP} / \text{Q}$ . Data were collected at a sampling frequency of 200 Hz and averaged over 5 successive beats. All parameters were extracted for the entire duration of baseline and bowel care, as well as for only the first 25 minutes of bowel care. Maximal responses were also determined during bowel care regardless of the time at which they occurred ( $\text{Parameter}_{\text{max}}$ ). AD was defined as an increase in  $\text{SAP}_{\text{max}}$  of at least  $20\text{mmHg}$  [29] compared to baseline. The overall burden of AD was determined from the area under the SAP curve (the product of SAP and heart beat).

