### **Statistical analyses**

Data processing was performed using R (Version 3.3.3) and RStudio (Version 1.1.453). Statistical analyses were performed using SigmaPlot 14 (Systat Software Inc., San Jose, CA). Data were tested for normality and parametric or non-parametric assumptions were used as appropriate. Comparisons of cardiovascular outcomes and symptoms between conditions (lidocaine and placebo) and test phases (baseline and during bowel care) were performed using two-way repeated measures ANOVA. Spearman rank correlations and

linear regressions were used to assess relationships between variables. Fisher's exact test was used to evaluate differences in proportions of responses between test conditions. Student t tests were used to compare responses between placebo and lidocaine conditions (e.g. time to complete bowel care). Statistical significance was assumed at  $p<0.05$ . Where appropriate, data are represented as mean  $\pm$  standard error, unless otherwise stated. Researchers, participants, care providers, and those analysing the data were blinded to the test condition. Researchers were unblinded just prior to statistical analyses.

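### Visit order was randomised 7/6, but no stated analysis includes period; a shift between visits would leave the tests valid but widen the intervals wherever baseline does not cancel it

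*Combined protocol and SAP*

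**What the plan says.** - **Design.** *Experimental Procedure* describes lidocaine and placebo lubricant given on two successive home visits, with order set by random draw: "seven participants were randomised to the lidocaine arm of the study first, and six to the placebo arm of the study first".
- **Baseline.** The same section places the baseline before the lubricant at each visit: "After a 10-minute baseline recording (sampling rate 200Hz) participants inserted 5mL of lubricant into the rectum using a specialised device". Duration has no baseline counterpart: at the end of the routine "the timer was stopped, and the bowel care duration noted".
- **Primary outcome and size.** *Participants* states: "Our primary outcome measure was the difference in systolic arterial pressure between the placebo and lidocaine conditions". The target is 10 mmHg, with power 0.8, alpha 0.05 and 13 people. No SD is given; the target is "based on previous unpublished observations from our lab".
- **Analysis.** *Statistical analyses* says that comparisons between conditions and "test phases (baseline and during bowel care) were performed using two-way repeated measures ANOVA". It adds: "Student t tests were used to compare responses between placebo and lidocaine conditions (e.g. time to complete bowel care", with the example closing there. Correlations, linear regressions and Fisher's exact test make up the rest. Neither period nor sequence appears in any of them.
- **Autonomic dysreflexia (AD).** In *Data analyses*, "AD was defined as an increase in" peak SAP of at least 20 mmHg over baseline.

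**The concern.** Order is the factor this trial randomised, yet the stated analysis does not use it. In a two-period crossover, any systematic change from visit 1 to visit 2 enters each person's lidocaine-minus-placebo difference with opposite signs in the two sequences. If period is not modelled, that spread is counted as random error.

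With 13 participants sized at exactly 80% power, there is little room for added error. The trial could miss the difference it was sized to find, or report an interval wider than the data require. Exposure varies by comparison: a baseline taken at the same visit removes some shifts but not others.

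**Working it through.** **Inputs from the documents.** N = 13, split 7/6; effect 10 mmHg; power 0.8; alpha 0.05.

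**Assumptions.** Two-sided paired t test on bowel-care SAP (the text does not say which test is primary, or that the t tests are paired). Normal differences. Visit-1-minus-visit-2 shift P of 0 to 10 mmHg.

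**Step 1: the plan's own figure.** N = 13 cannot be reproduced because no SD is given. Solving backwards for the SD of the paired differences gives 11.8 mmHg (noncentral t, two-sided), 12.9 (normal approximation, two-sided) or 13.7 (noncentral t, one-sided). The first is used below, and the others test sensitivity.

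**Step 2: effect of the shift.** Write dᵢ = 10 + sᵢP + eᵢ, with sᵢ = +1 for seven people and −1 for six.
- Bias = P × (7 − 6)/13 = P/13.
- Added variance = P² × (13 − 1/13)/12 = 1.077 × P².
- Unadjusted 95% half-width = 2.179 × √(11.81² + 1.077P²)/√13, on 12 df.
- Adjusted estimate = average of the two sequence means. Half-width = 2.201 × 11.81 × √[(1/7 + 1/6)/4] = 2.201 × 11.81 × 0.278 = 7.2 mmHg, on 11 df, for any P.

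Setting the two half-widths equal gives P = 0.157 SD = 1.9 mmHg. Below that, adjustment does not narrow the interval.

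**Step 3: power and error rate by simulation, SD 11.8.** Favourable means that the shift enlarges the estimated effect.

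| Shift P (mmHg) | 0 | 2.5 | 5 | 10 |
|---|---|---|---|---|
| Bias (mmHg) | 0 | 0.2 | 0.4 | 0.8 |
| Half-width, unadjusted (mmHg) | 7.1 | 7.3 | 7.8 | 9.5 |
| Power, unadjusted, favourable | 80% | 80% | 78% | 65% |
| Power, unadjusted, unfavourable | 80% | 77% | 71% | 49% |
| Power, with period | 79% | 79% | 79% | 79% |
| Type I error, unadjusted, at 7/6 | 5.0% | 4.6% | 3.5% | 1.3% |

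Adjustment starts to gain power at about 4 mmHg (favourable) or 1 mmHg (unfavourable).

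**Step 4: sensitivity to the SD.** Powers are for shifts of 0/2.5/5/10 mmHg.
- SD 12.9: 73/73/71/59% favourable, 73/70/64/44% unfavourable, against 72% adjusted.
- SD 13.7: 68/68/66/55% favourable, 68/65/59/41% unfavourable, against 67% adjusted.
- If 11.8 already contains a 5 mmHg shift, the residual SD is √(11.81² − 1.077 × 25) = 10.6. Power is then 85% or 79% unadjusted, against 87% adjusted.

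**Step 5: the other comparisons.** The two-phase model takes SD 11.8 for the between-condition difference at each phase, with an assumed correlation between phases.
- *Condition main effect.* Baseline precedes the lubricant, so averaging over phases dilutes 10 mmHg to 5 mmHg. At correlations 0/0.5/0.8, power is 51/37/32% with no shift and 50/36/31% adjusted. A 5 mmHg shift in both phases gives about 43/33/29% (favourable) or 32/25/22% (unfavourable). Adjustment recovers the loss from the shift but not the dilution.
- *Condition-by-phase interaction, and AD as a rise from baseline.* A shift common to both phases subtracts out, so interaction power stays at 80% (correlation 0.5). A shift only in the response to bowel care does not: interaction power is 78% or 71% at 5 mmHg and 65% or 49% at 10 mmHg, against 79% adjusted.
- *Duration.* It has no baseline, and no figure in minutes can be derived. In units of the SD of its paired differences, a shift of 0/0.25/0.5/1 SD gives an unadjusted half-width of 0.604/0.624/0.681/0.871, against 0.612 adjusted. That is 1% narrower, then 2%, 11% and 42% wider.

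**The case against.** The best reply is that the harm is hypothetical. The participants had chronic injury and an established routine and were studied at home under usual care; nothing in the text points to a visit effect or its size. The lowest powers need a shift as large as the whole target effect. Averaged over the two directions, unadjusted power is about 78.6% at 2.5 mmHg and 74.1% at 5 mmHg, against 79% adjusted, so small shifts matter little. For pressure, the stated model includes a same-visit baseline, and the interaction, arguably its informative contrast, is immune to a common shift. Duration is not the primary outcome. Testing ended in October 2018, so only a post hoc analysis may now be possible.

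All of this is fair and limits the size of the point. It does not remove it. First-visit unfamiliarity with the monitoring is not excluded. The interaction is not named as the primary test, whereas the primary outcome is worded as a direct between-condition difference in SAP. Duration is explicitly given a t test with nothing to cancel a shift.

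One qualification should be kept. The fall in type I error below 5% holds given the realised 7/6 split. Over repeated independent draws of sequence, the unadjusted test rejects at 5.0 to 5.1% for shifts of 0 to 10 mmHg. It is valid on either view.

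**Conclusion.** The concern holds, as one of precision and not of validity. The omission is certain from the text; its consequence depends on a shift that the documents neither report nor rule out.

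For bowel-care SAP, a 5 mmHg shift costs about 1 or 8 power points relative to adjustment, and a 10 mmHg shift about 14 or 30, depending on direction. Bias stays under 1 mmHg over that range. These figures rest on a paired test, a 10 mmHg effect and a back-solved SD of 11.8 mmHg; the pattern is the same at 12.9 and 13.7. The condition main effect and duration are also exposed. The interaction and AD measured from baseline are exposed only to a shift in the response to bowel care. The change is worth making because it is cheap, with medium confidence that it would matter in these data. Carryover is a separate question and was not assessed.

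**What to change.** - Add period (visit 1 or 2) as a fixed effect with participant random. Add period-by-phase where baseline is part of the comparison, and keep the repeated measures error terms.
- For single-value outcomes such as duration, use a two-sample t test between sequences on the visit-1-minus-visit-2 differences. The treatment estimate is half the difference between the sequence means.
- Report the period effect with its 95% interval, and do not drop the term because it is non-significant. At SD 11.8 its half-width is itself about 7.2 mmHg, so a non-significant result would not show that there was no shift.
- Use the rank-sum version only as a sensitivity analysis. With no shift its power is 70%, against 78% for the signed-rank test, and its exact size at 7 v 6 is 3.5%.
- If the analysis is complete, present the period-adjusted results beside the stated ones, labelled as a post hoc sensitivity analysis.

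**Cost.** One degree of freedom and about 1 power point (80% to 79%) if there is no shift. Visit order is already known, so no new data are needed, only a reanalysis if results exist.

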### **Autonomic dysfunction**

Severity of autonomic dysfunction was determined through spectral analyses of low-frequency systolic arterial pressure variability (LF SAP). LF SAP oscillations ( $\sim 0.1\text{Hz}$ ) reflect sympathetic control of the vasculature, and thus indicate the presence or absence of autonomic cardiovascular control following SCI [26]. Participants with LF SAP lower than  $3.75\text{mmHg}^2$  were determined to have autonomically-complete injuries.

### **Cardiac rate and rhythm analyses**

Electrocardiogram data were visually inspected offline after completion of the study. The number of beats that met criteria for bradycardia ( $<60\text{bpm}$ ) and tachycardia ( $>100\text{bpm}$ ) was determined during baseline and bowel care, and expressed as a percentage of the total number of beats in the corresponding phase. In addition, each beat was classified as either sinus rhythm, or not, and any arrhythmia or conduction abnormalities noted.

### **Data analyses**

Beat-to-beat systolic (SAP) and diastolic (DAP) arterial pressures were extracted throughout the testing period. Mean arterial pressure (MAP) was calculated as  $\text{DAP} + 1/3 \times (\text{SAP}-\text{DAP})$ . Heart rate was determined from the R-R interval of the ECG. Stroke volume (SV) and cardiac output (Q) were determined using Modelflow [27,28], and total peripheral resistance (TPR) calculated as  $\text{MAP} / \text{Q}$ . Data were collected at a sampling frequency of 200 Hz and averaged over 5 successive beats. All parameters were extracted for the entire duration of baseline and bowel care, as well as for only the first 25 minutes of bowel care. Maximal responses were also determined during bowel care regardless of the time at which they occurred ( $\text{Parameter}_{\text{max}}$ ). AD was defined as an increase in  $\text{SAP}_{\text{max}}$  of at least  $20\text{mmHg}$  [29] compared to baseline. The overall burden of AD was determined from the area under the SAP curve (the product of SAP and heart beat).

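### MAP is computed by the one-third rule although the 200 Hz recording very probably allows a mean for each beat: a minor, cheaply avoided error confined to MAP and TPR

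*Combined protocol and SAP*

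**What the plan says.** Under Data analyses, the plan works from two pressures per beat: "Beat-to-beat systolic (SAP) and diastolic (DAP) arterial pressures were extracted throughout the testing period". It then states "Mean arterial pressure (MAP) was calculated as" DAP plus one third of the difference between SAP and DAP. The same section has "total peripheral resistance (TPR) calculated as" MAP / Q. It gives no reason for the approximation and mentions no mean taken from the waveform.

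The recording is described in two places. Experimental Procedure names a "non-invasive beat-to-beat finger blood pressure monitor" and a 200 Hz sampling rate. Data analyses repeats the rate: "Data were collected at a sampling frequency of 200 Hz and averaged over 5 successive beats". It also says "Stroke volume (SV) and cardiac output (Q) were determined using Modelflow", so Q does not come from the MAP formula.

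Statistical analyses compares cardiovascular outcomes by condition and by phase with a two-way repeated measures ANOVA. It does not list them by name, but MAP and TPR read as being among them. The primary outcome is elsewhere, under Participants: "Our primary outcome measure was the difference in systolic arterial pressure between the placebo and lidocaine conditions".

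**The concern.** The one-third rule is a stand-in for when only SAP and DAP are known. Here the pressure signal was sampled 200 times a second, so the stand-in looks unnecessary.

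Two things follow from using it. First, MAP becomes exactly 2/3 DAP + 1/3 SAP, so a MAP comparison adds no measured information beyond the two pressures already analysed. Second, the rule gives every beat the same waveform shape. If the real shape differs from that, part of a MAP or TPR difference between phases or conditions reflects pulse pressure or waveform shape and not mean pressure. The trial asks whether lidocaine changes the pressure response, so equal pulse pressure at the two visits cannot be taken for granted.

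**Working it through.** **No figure to reproduce.** The plan states no accuracy for MAP or TPR. Its one numerical design target, a 10 mmHg difference with 13 participants, concerns SAP and does not involve MAP.

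**Inputs from the documents.** The MAP and TPR formulas, the 200 Hz rate, and Q from Modelflow.

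**Inputs assumed.** The documents give neither a form factor nor a pulse pressure. I take k from 0.30 to 0.45, and illustrative pressures of 110/70 (PP 40), 150/80 (PP 70) and 180/90 (PP 90).

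**Formula.** Let PP = SAP − DAP and let the waveform mean be DAP + k × PP. The rule gives DAP + PP/3. So

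- understatement of MAP = (k − 1/3) × PP (a negative value means MAP is overstated);
- relative error in TPR = relative error in MAP, because Q is obtained separately.

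Averaging over 5 beats does not remove the error, because the rule is linear in SAP and DAP.

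**Single-state error and contrast error, in mmHg of MAP understated**

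| k | PP 40 | PP 70 | PP 90 | PP 90 with DAP 90, % of MAP and TPR | Contrast, per 10 mmHg PP difference |
|---|---|---|---|---|---|
| 0.30 | −1.3 | −2.3 | −3.0 | −3.0/117.0 = −2.6% | −0.33 |
| 1/3 | 0 | 0 | 0 | 0 | 0 |
| 0.36 | 1.1 | 1.9 | 2.4 | 2.4/122.4 = 2.0% | 0.27 |
| 0.40 | 2.7 | 4.7 | 6.0 | 6.0/126.0 = 4.8% | 0.67 |
| 0.45 | 4.7 | 8.2 | 10.5 | 10.5/130.5 = 8.0% | 1.17 |

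**Contrast between conditions.** With the same k at both visits, the lidocaine-placebo MAP contrast is off by (k − 1/3) × the difference in PP, which is the last column. For scale, suppose the 10 mmHg SAP difference in the sample-size statement fell entirely on PP with DAP unchanged. The rule would report a MAP difference of 10/3 = 3.33 mmHg. The waveform mean would differ by 3.0 (k = 0.30), 4.0 (k = 0.40) or 4.5 mmHg (k = 0.45). If DAP moved with SAP, the PP difference and hence the error would be smaller.

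**If k changes between the states compared.** Take PP rising from 40 to 70:

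- k constant at 0.40: understatement 2.7 to 4.7, so the rise in MAP is 2.0 mmHg too small.
- k from 0.36 to 0.40: 1.1 to 4.7, so the rise is 3.6 mmHg too small.
- k from 0.40 to 0.36: 2.7 to 1.9, so the error shrinks although PP widens.
- k from 0.40 to 1/3: 2.7 to 0.

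The error cancels only where (k − 1/3) × PP is equal in the two states compared.

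**The case against.** The strongest reply is that this is a disclosed, conventional formula, applied identically in both conditions of a within-person crossover, to variables on which no key result depends. Most of that stands. Error common to both visits cancels, and at constant k what remains is about 1 mmHg or less per 10 mmHg of pulse-pressure difference. The primary outcome is SAP. AD is defined by a rise in maximal SAP, AD burden is the area under the SAP curve, and autonomic completeness uses LF SAP. No threshold or decision is attached to MAP or TPR.

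A reader might infer something stronger: that the error necessarily grows as pulse pressure widens during AD. The documents do not support this. They report no pulse pressure, do not say that it widens in AD, and give no form factor. Growth is assured only if k is constant and differs from 1/3. The assumed range includes 1/3 and changes sign there, and a fall in k can shrink the error while pulse pressure rises.

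Two further cautions are fair. That the full waveform was stored is a strong inference from the 200 Hz rate and the use of Modelflow, not a statement in the plan. And the integral of this signal is mean finger pressure, which the documents do not validate as the true arterial mean.

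The objection does not show that the approximation was needed. Cancellation is only partial wherever pulse pressure or waveform shape differs between conditions or phases, and the recordings themselves could settle the question.

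**Conclusion.** A minor, valid point about MAP and TPR only. The plan approximates a quantity that its own recording very probably supplies. The size and sign of the resulting error cannot be established from the documents.

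Under an assumed k of 0.30 to 0.45, equal at both visits, the treatment contrast in MAP is off by about −0.3 to +1.2 mmHg per 10 mmHg difference in pulse pressure. The single-state error at DAP 90 and pulse pressure 90 is −3.0 to +10.5 mmHg of MAP understated, up to about 8% of MAP and TPR. If k also shifts between the states compared, the contrast error can be larger or smaller than the constant-k figure.

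The plan does not show that the trial's main findings are biased. The primary SAP comparison, the AD definition, AD burden, the LF SAP classification and the sample size do not use MAP.

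**What to change.** Where the waveforms are retained, replace the MAP sentence with wording such as:

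> MAP for each beat is the time-average of the recorded finger pressure over that beat, averaged in the same way as the other parameters; TPR is this MAP divided by Q. Values from the one-third rule are reported as a sensitivity analysis.

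If the waveforms were not kept, say so, give that as the reason for the approximation, and note that MAP and TPR carry an error that depends on pulse pressure and waveform shape.

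The cost is modest reprocessing of existing recordings: beat detection and artefact checks on unstandardised home recordings, with the rules applied without reference to condition. No new visits, participants or measurements are needed. The gain is limited in two ways: the result is mean finger pressure, and TPR still rests on a model-based Q.

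### Overall AD burden is written as an area under absolute SAP although AD is defined as a rise from baseline, so resting pressure and beat count enter the score

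*Combined protocol and SAP*

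**What the plan says.** In Data analyses, an AD event is a peak SAP that exceeds baseline by 20 mmHg or more. The burden measure follows directly: "compared to baseline. The overall burden of AD was determined from the area under the SAP curve". The only further detail is the bracketed gloss, so the full definition is the "area under the SAP curve (the product of SAP and heart beat". No subtraction, threshold or divisor is given.

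The same section extracts parameters over all of baseline and all of bowel care, "as well as for only the first 25 minutes of bowel care", but does not say which window the burden score uses. Under Experimental Procedure, "Bowel care routines were not standardised", so care length can differ between visits. That section also provides a 10-minute baseline recording at each visit, before the lubricant is inserted.

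Elsewhere the plan does scale by exposure. Under Cardiac rate and rhythm analyses, counts of slow and fast beats are "expressed as a percentage of the total number of beats in the corresponding phase".

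Statistical analyses describes a condition-by-phase repeated measures ANOVA for cardiovascular outcomes, and t tests for comparing conditions. Burden is not named under either.

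**The concern.** The event is relative to baseline, but its burden, as written, is absolute. Most of an absolute area is resting pressure multiplied by the number of beats. The crossover removes whatever part of that is the same at a participant's two visits. It does not remove a difference between the visits, and any such difference is then read as more or less AD.

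Three quantities unrelated to AD can move the score: resting SAP on the day, the number of beats in the window and, if whole care is used, how long care lasted. What is at stake is the meaning of the lidocaine-placebo comparison of AD burden. The primary SAP outcome, peak SAP and AD incidence are separate measures and are not affected.

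**Working it through.** The plan gives no figure for burden, so there is none to reproduce. Its sample size of 13 concerns the primary outcome and does not enter here.

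**Inputs from the documents:** the baseline-referenced definition of AD; a 10-minute baseline per visit; the 25-minute window; and, from Participants, a "meaningful difference to detect in blood pressure between the two study arms of 10mmHg", used below as a yardstick. **Assumed, because the documents give none:** every resting pressure, rise, heart rate, whole-care duration and SD.

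**Formulas.** Let B = resting SAP, r = mean rise, H = beats per minute and T = minutes.
- Score as written: (B + r) × H × T.
- Baseline-referenced area over time: r × T.

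**1. No rise.** 120 × 70 × 25 = 210,000, with no AD at all.

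**2. Resting SAP differs between visits (70 bpm, 25 min).** A true 10 mmHg effect adds 10 × 70 × 25 = 17,500. Resting differences add:
- 2 mmHg: 2 × 70 × 25 = 3,500 (20% of 17,500)
- 5 mmHg: 5 × 70 × 25 = 8,750 (50%)
- 10 mmHg: 10 × 70 × 25 = 17,500 (100%)

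These percentages are simply the resting difference divided by 10; heart rate and window cancel.

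**3. A halved rise can be hidden.** With B = 110, r = 20, H = 65 and T = 25, the score is 130 × 65 × 25 = 211,250. Of this, 20 × 65 × 25 = 32,500 (15.4%) is rise. With B = 120 and r = 10, the score is again 130 × 65 × 25 = 211,250, although the rise part has halved to 10 × 65 × 25 = 16,250.

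**4. Heart rate.** Let P be the SAP in the higher-pressure condition and P − 10 in the other. The scores are equal when the rate in the higher condition is lower by the fraction 10/P:
- P = 110: 9.1%, or 6.4 bpm on 70
- P = 140: 7.1%, or 5.0 bpm
- P = 160: 6.25%, or 4.4 bpm

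Beyond break-even the order reverses: 140 × 60 × 25 = 210,000 against 130 × 70 × 25 = 227,500. This example uses a 10 bpm gap, twice the 5.0 bpm break-even. Above a common baseline of 120, the time-based areas are 20 × 25 = 500 and 10 × 25 = 250 mmHg·min, the right order.

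If baseline is subtracted but beats are kept as the axis, some dependence remains. The rate fall that cancels 10 mmHg becomes 10 divided by the larger rise: 50% for a rise of 20, 25% for 40, 12.5% for 80.

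**5. Whole care, only if that window was used.** Each extra minute at 120 mmHg and 70 bpm adds 120 × 70 = 8,400 with no AD. On 40 minutes of care, the extra minutes that cancel 10 mmHg are 40 × 10 / (lower SAP): 4.0 at 100, 3.1 at 130, 2.7 at 150. For a baseline-referenced time area they are 40 × 10 / (smaller rise): 40 for a rise of 10, 13.3 for 30, 5.7 for 70. Subtraction weakens the dependence on duration but does not remove it.

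**6. Zero floor or signed difference.** If values below baseline were set to zero, a visit with no mean rise would score SD × 0.399 under normality: 2.0, 4.0 or 6.0 mmHg for a within-visit SD of 5, 10 or 15. A signed difference has expectation zero in each case.

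**7. Precision.** Subtraction lowers the variance of a visit-level score only if the baseline-care correlation exceeds 0.5 × SD(baseline) / SD(care), because Var(C − b) = Var(C) + Var(b) − 2·Cov(C, b), where C is care SAP and b baseline SAP. The documents give none of these quantities.

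**The case against.** **It is one terse sentence, and an unreported correction may exist.** This stands in part. If a baseline-referenced area was computed, only the text needs changing. If heart beat meant R-R duration, the axis is already time and the beat-count point lapses; that reading would fit "Heart rate was determined from the R-R interval of the ECG". Neither reading puts a baseline into the stated rule.

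**The same resting shift moves any absolute mean SAP, including the primary outcome.** The arithmetic is right. But the primary outcome is named as a pressure difference, and resting pressure is part of pressure. Burden is named as AD, which the plan itself defines as a rise.

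**The phase factor in the ANOVA supplies a baseline reference.** It would do so only if burden were analysed there, and it is not named. Unscaled areas over a 10-minute baseline and over care of another length would not be comparable anyway.

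**Subtraction may not improve precision.** This stands, as step 7 shows. The case for subtraction is that the score would then measure the rise.

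**AD incidence is already baseline-referenced.** True, but incidence records whether a threshold was crossed, not how much pressure rise accumulated.

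A reader might go further and infer that the burden comparison is biased or came out in the wrong order. The documents do not support that: order was randomised (seven participants received lidocaine first, six placebo), so visit differences mainly add noise unless they differ by condition. Misranking is shown to be possible, not to have occurred.

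**Conclusion.** The point holds for the rule as written, and it should be fixed. The stated score does not isolate the quantity it is named for: a visit with no rise scores highly, and resting SAP and beat count move the result. On assumed values, modest visit differences are large beside the plan's 10 mmHg yardstick: 5 mmHg of resting SAP is worth half of it, and a 6-9% difference in heart rate can cancel it. The direction of these effects does not depend on the assumed values; their size does. Dependence on care length is conditional on whole care having been the window.

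The consequence is limited to a non-primary measure, and mainly to added noise. A reader might infer that the trial's main pressure result is undermined. It is not, because the primary SAP outcome, peak SAP and AD incidence do not use this score.

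**What to change.** If a baseline-referenced area was in fact used, say so and state its axis and window. Otherwise:

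- Derive burden as the signed difference between SAP and that visit's 10-minute baseline mean, integrated over time, with each 5-beat mean weighted by its R-R duration and no zero floor.
- Report it per minute over the first 25 minutes, or to the end of care if shorter. This is a time-weighted mean rise in mmHg. Also report the whole-care area in mmHg·min, alongside care duration.
- Compare it between conditions only; the baseline phase averages about zero by construction.
- Label it post hoc. "Testing took place between August 2016 and October 2018", so it is defined after testing ended, and after unblinding too if that has occurred. Show the score as documented beside it.
- Leave the primary SAP outcome, peak SAP and AD incidence as they are.

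**Cost:** re-scripting one derived variable from beat-to-beat data and baselines already held, and reporting extra versions of a non-primary measure. No new data are needed. **Downsides:** subtraction adds the baseline's own measurement noise, so a gain in precision is not guaranteed; time below baseline offsets time above it; and a post hoc definition carries less weight than a prespecified one.
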